1.1.1.2.1. Maintenance Primary Estimand (Hybrid)

The maintenance primary estimand is a hybrid estimand representing the clinical question of interest: what is the response proportions or means for each treatment condition (i.e., Lebrikizumab 250 mg Q2W and Lebrikizumab 250 mg Q4W), in the target participant population, in successful responses or means after 68 weeks achieved without use of systemic rescue medication, without transferring to escape arm, if topical rescue medication were not available and if all participants continued with treatment except those who discontinued due to lack of efficacy?

The maintenance primary estimand is described by the following attributes:

- A. Population: Maintenance Primary Population (MPP) as described in Section 3
- B. Endpoint: apply to key categorical and continuous endpoints (i.e., Investigator's Global Assessment [IGA], Eczema Area and Severity Index [EASI] and Itch Numeric Rating Scale [NRS] related endpoints) for the Maintenance Period
- C. How to account for ICEs
 - a. Participants who require any use of systemic rescue medication, discontinue treatment due to lack of efficacy after Week 16, or transfer to escape arm will be considered as treatment failures, i.e., non-responder, after the ICEs. Therefore, composite strategy is used for these types of ICEs.
 - b. For participants who require any use of topical rescue medication, a hypothetical strategy will be used to estimate what the response proportions or means for each treatment condition would have been if participants continued with treatment. Therefore, hypothetical strategy is used for these types of ICEs.
 - c. For participants who discontinue treatment due to reasons other than lack of efficacy after week 16, a hypothetical strategy will be used to estimate what the response proportions or means for each treatment condition would have been if participants continued with treatment. Therefore, hypothetical strategy is used for these types of ICEs.
- D. Population-level summary: response proportions or means for each treatment condition

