1.1.1.2.4. Maintenance Supportive Estimand for Continuous Endpoints (Hypothetical)

The maintenance supportive estimand for continuous endpoints only is a hypothetical estimand representing the clinical question of interest: what is the means for each treatment condition (i.e., Lebrikizumab 250 mg Q2W and Lebrikizumab 250 mg Q4W), in the target participant population, in means after 68 weeks if rescue medication was not available and all participants adhered to the treatment and did not transfer to escape arm?

The maintenance supportive estimand is described by the following attributes:

- A. Population: MPP as described in Section 3
- B. Endpoint: apply to all continuous endpoints for the Maintenance Period
- C. How to account for ICEs
 - a. For participants who require any use of rescue medication, discontinue treatment after Week 16, or transfer to escape arm, a hypothetical strategy will be used to estimate what the means for each treatment condition would have been if rescue medication was not available and all participants adhered to the treatment and did not transfer to escape arm. Therefore, hypothetical strategy is used for these types of ICEs.
- D. Population-level summary: means for each treatment condition

Details on how missing data including those as a result of intercurrent events will be handled can be found in Section 4.1.6.2. Detailed analyses relative to estimands including analysis type, method and imputation, population, time point, and treatment comparisons for efficacy and health outcome analyses can be found in [Appendix 2](#).

The table below summarizes the analytical strategies that will be conducted on the intercurrent events for the four maintenance estimands. Intercurrent events and missing data will be summarized by treatment group for the Induction Period on the ITT population, and for the Maintenance Blinded Period on the MPP, respectively.

Description of Primary and Supportive Estimands for Maintenance Period

Maintenance Estimand	Analysis Strategy for Intercurrent Events				Transfer to Escape Arm	Missing Data Imputation Method		
	Rescue Medication		Treatment Discontinuation					
	Topical rescue medication	Systemic rescue medication	Due to lack of efficacy	Due to any other reasons				
Maintenance Primary Estimand (Hybrid)	Hypothetical: Set to missing	Composite: Set to baseline	Composite: Set to baseline	Hypothetical: Set to missing	Composite: Set to baseline	Primary analysis: MCMC-MI		

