4.1.2.1. Maintenance Primary and Secondary Population

The number and percentage of participants achieving or maintaining categorical efficacy and health outcome responses will be summarized by treatment group for all scheduled visits, including Week 68.

Each continuous efficacy and health outcome measure score and the change from baseline (or percentage improvement) will be summarized by treatment group at all scheduled visits during the Maintenance Period, including Week 68 using descriptive statistics (n, mean, SD, median, minimum, and maximum). No inferential statistics will be provided for these populations.

For the MPP, the KM product limit method will be used to estimate the survival for time to event analyses (e.g., time to loss of IGA score of 0 or 1, or loss of EASI-50). A KM plot of the time to event by treatment group may be provided.

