6.1. Appendix 1: Description and Derivation of Efficacy and Health Outcome Endpoints

Description and Derivation of Efficacy/Health Outcome Measures and Endpoints

Measure	Description	Variable	Derivation/Comment	Imputation Approach if Missing Components
Investigator's Global Assessment (IGA)	
The IGA is a static assessment and rates the severity of the participant's AD.
 
The IGA is comprised of a 5-point scale ranging from 0 (clear) to 4 (severe) and a score is selected using descriptors that best describe the overall appearance of the lesions at a given time point.
	IGA score	Single item. Range: 0 to 4 0 represents "clear" 4 represents "severe"	Single item, missing if missing.
		Change from baseline in IGA score	Change from baseline: observed IGA score – baseline IGA score	Missing if baseline or observed value is missing.
		IGA (0,1) with \geq 2-point improvement	Observed score of 0 or 1 and change from baseline ≤ -2	Missing if baseline or observed value is missing.
		IGA (0)	Observed score of 0	Single item, missing if missing.
		Time to loss of IGA response, i.e., developing an IGA score ≥ 2 with 2 points deterioration of achieved IGA response at Week 16	Date of first time developing an IGA score ≥ 2 with 2 points deterioration of achieved IGA response at Week 16 – date of Week 16 + 1	
If a participant has not experienced loss of response by completion or early discontinuation of the Maintenance Blinded Period, the participant will be censored at the date of their last visit during the Maintenance Blinded Period.
 
If a participant has not experienced loss of response by the time of systemic rescue, the participant will be censored at the date of systemic rescue.

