		Change from baseline in each symptom score and percentage involvement	Change from baseline: observed score – baseline score	Missing if baseline or observed value is missing.

		score by body regions in EASI		
		EASI-50	% Improvement in EASI score from baseline $\geq 50\%$: % change from baseline ≤ -50	Missing if baseline or observed value is missing.
		EASI-75	% Improvement in EASI score from baseline $\geq 75\%$: % change from baseline ≤ -75	Missing if baseline or observed value is missing.
		EASI-90	% Improvement in EASI score from baseline $\geq 90\%$: % change from baseline ≤ -90	Missing if baseline or observed value is missing.
		Time to loss of EASI-50	Date of first time % change from baseline in EASI score > -50 – date of Week 16 + 1	If a participant has not experienced loss of response by completion or early discontinuation of the Maintenance Blinded Period, the participant will be censored at the date of their last visit during the Maintenance Blinded Period. If a participant has not experienced loss of response by the time of systemic rescue, the participant will be censored at the date of systemic rescue.

		Time to loss of EASI-75	Date of first time % change from baseline in EASI score > -75 – date of Week 16 + 1	If a participant has not experienced loss of response by completion or early discontinuation of the Maintenance Blinded Period, the participant will be censored at the date of their last visit during the Maintenance Blinded Period. If a participant has not experienced loss of response by the time of systemic rescue, the participant will be censored at the date of systemic rescue.
Body Surface Area (BSA)	The BSA assessment estimates the extent of disease or skin involvement with respect to AD and is expressed as a percentage of total body surface. BSA will be determined by the Investigator or designee using the participant palm = 1% rule.	BSA	Use the percentage of skin affected for each region (0 to 100%) in EASI as follows: BSA Total = 0.1*BSAhead and neck + 0.3*BSAtrunk + 0.2*BSAupper limbs + 0.4*BSAlower limbs	N/A – partial assessments cannot be saved.
		Change from baseline in BSA	Change from baseline: observed BSA score – baseline BSA score	Missing if baseline or observed value is missing.

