	Time to loss of EASI-50	N/A	KM method	MPP	No comparisons.	Secondary analysis
	Time to loss of EASI-75	N/A	KM method	MPP who have achieved EASI-75 at Week 16	No comparisons.	Secondary analysis
	Proportion of participants with EASI-75	N/A	Descriptive statistics	MSP	No comparisons. All scheduled visits in the Maintenance Period	Secondary analysis
	Proportion of participants with EASI-75	N/A	Descriptive statistics	Maintenance W16 Escape Population	No comparisons. All scheduled visits in the Maintenance Period	Secondary analysis

Measure	Variable	Estimand (Section 1.1.1)	Analysis Method (Section 4.1)	Population (Section 3)	Comparison/Time Point	Analysis Type
	Proportion of participants with EASI-75 after lebrikizumab re-treatment	N/A	Descriptive statistics	Maintenance Period W20-64 Escape Population	No comparisons. Every 4 weeks after escape and re-treated by lebrikizumab 250 mg Q2W	Secondary analysis
Body Surface Area (BSA) Affected by AD	Change from baseline in BSA	Supportive Estimand (Hypothetical)	MMRM	ITT	Leb 250 mg Q2W vs PBO; Leb 250 mg Q4W vs PBO; Week 16 and all scheduled visits in the Induction Period	Secondary analysis
		Maintenance Supportive Estimand (Hypothetical)	Descriptive statistics with LOCF	MPP	No comparisons. All scheduled visits in the Maintenance Period	Secondary analysis
		N/A	Descriptive statistics	Maintenance W16 Escape Population	No comparisons. All scheduled visits in the Maintenance Period	Secondary analysis
Itch Numeric Rating Scale (NRS)	Change from baseline in Itch NRS prorated weekly mean score	Primary Estimand (Hybrid)	ANCOVA with MCMC-MI	ITT	Leb 250 mg Q2W vs PBO; Leb 250 mg Q4W vs PBO; Week 16 and all scheduled visits in the Induction Period	Secondary analysis
		Supportive Estimand (Hypothetical)	MMRM	ITT	Leb 250 mg Q2W vs PBO; Leb 250 mg Q4W vs PBO; Week 16 and all scheduled visits in the Induction Period	Supplementary analysis
	Percentage change from baseline in Itch NRS prorated weekly mean score	Maintenance Primary Estimand (Hybrid)	Descriptive statistics with MCMC-MI	MPP	No comparisons. All scheduled visits in the Maintenance Period	Secondary analysis
		Maintenance Supportive Estimand (Hybrid)	Descriptive statistics with MCMC-MI			Supplementary analysis

Measure	Variable	Estimand (Section 1.1.1)	Analysis Method (Section 4.1)	Population (Section 3)	Comparison/Time Point	Analysis Type
		Maintenance Supportive Estimand (Hypothetical)	Descriptive statistics with LOCF			Supplementary analysis

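### Time to loss of EASI-50, EASI-75 and IGA response censors events that the SAP's primary maintenance estimand counts as treatment failure, and no curve that counts them is planned

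*SAP*

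**What the plan says.** SAP Section 6.1 (Appendix 1) gives the same two censoring rules for time to loss of IGA response, EASI-50 and EASI-75. The first applies to anyone who finishes the blinded part of maintenance, or leaves it early, with no recorded loss: "the participant will be censored at the date of their last visit during the Maintenance Blinded Period". It does not distinguish reasons for discontinuation. The second covers a participant with no loss before systemic rescue: "the participant will be censored at the date of systemic rescue".

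SAP Section 4.1.2.1 names the estimator for the Maintenance Primary Population: "the KM product limit method will be used to estimate the survival for time to event analyses". In SAP Section 6.2 (Appendix 2), the row "Time to loss of EASI-50" and the corresponding EASI-75 and IGA rows give the estimand as N/A and plan no comparisons. SAP Section 1.1 lists all three as Other Secondary endpoints.

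The maintenance primary estimand (SAP Section 1.1.1.2.1) takes a different view of these events. "Participants who require any use of systemic rescue medication, discontinue treatment due to lack of efficacy after Week 16, or transfer to escape arm" are non-responders from that point on. The summary table that closes SAP Section 1.1.1.2 shows "Composite: Set to baseline" for all three events in both hybrid estimands, and non-response in the composite estimand. Only the hypothetical estimand, which is for continuous endpoints, sets them to missing.

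**The concern.** Kaplan-Meier estimation assumes that a censored participant has the same future risk of loss as those still followed. That is doubtful here. Protocol Section 6.5.3 links rescue to intolerable worsening and requires study discontinuation when long-term systemic treatment for AD is needed in the Maintenance Period. Systemic rescue and drop-out for lack of efficacy are therefore usually signs of failing disease control, not neutral ends of follow-up.

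Durability on Q2W and Q4W is a stated purpose of the maintenance design (Protocol Section 4.3), and these curves are what a reader will consult for it. As specified, they answer how long response lasts if failing participants are assumed to carry on like those still responding. The SAP does not state that question, since the estimand is N/A. It also plans no second curve that counts these events as loss.

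**Working it through.** **No figure to reproduce.** Neither document states an event count, loss rate or precision for these endpoints. The check therefore compares the rules, derives the direction, and then bounds the size.

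**Step 1: the rules side by side, for a participant with no earlier recorded loss.**

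| Event in maintenance | Primary maintenance estimand | KM, EASI-50 and EASI-75 | KM, IGA |
|---|---|---|---|
| Systemic rescue | Failure | Censored at rescue | Censored at rescue |
| Discontinuation, lack of efficacy | Failure | Censored at last blinded visit | Censored at last blinded visit |
| Transfer to Escape Arm | Failure | Already an event | Event only if IGA is ≥2 and 2 points worse than at Week 16; otherwise censored |
| Discontinuation, other reason | Hypothetical (set to missing) | Censored | Censored |

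Escape after Week 16 requires loss of EASI-50 (Protocol Section 4.1), which also means loss of EASI-75. The escape visit is therefore itself the EASI event. IGA differs. A participant at IGA 1 at Week 16 who moves to IGA 2 and falls below EASI-50 enters the Escape Arm having worsened by 1 point. Only data up to escape are used (SAP Section 4.1.2), so this participant is censored for IGA.

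**Step 2: direction.** If r participants are at risk when one such failure occurs, counting it as an event multiplies the curve from then on by (1 − 1/r). Censoring leaves the curve unchanged at that time. The censored curve can therefore never lie below the composite one.

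**Step 3: weight of one participant.** Arm sizes follow from the Week 16 rates in SAP Section 5 and the 1:1 re-randomisation. With no other censoring, the gap is at most 1/n per such participant.

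- EASI-75 responders, Q2W: 0.58 × 120 = 69.6, or 34.8 per re-randomised arm; 1/34.8 = 2.9 points.
- EASI-75 responders, Q4W: 0.53 × 80 = 42.4; 1/42.4 = 2.4 points.
- IGA responders, Q2W: 0.38 × 120 = 45.6, or 22.8 per arm; 1/22.8 = 4.4 points.
- IGA responders, Q4W: 0.33 × 80 = 26.4; 1/26.4 = 3.8 points.

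Time to loss of EASI-50 uses the whole Maintenance Primary Population, which is somewhat larger than the EASI-75 group, so one participant weighs slightly less there.

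**Step 4: illustration on assumed rates.** Take n = 35 and 13 four-weekly steps (52/4), with recorded losses and failures spread evenly. Per step, d = n × loss/13 and c = n × failures/13. The censored curve multiplies by (1 − d/r) and the composite by (1 − (d + c)/r); r then falls by d + c. The composite ends at 1 − loss − failures.

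With 20% recorded loss, retention at Week 68 is:

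| Rescue or lack-of-efficacy drop-out, no recorded loss | Failures censored | Failures counted | Gap (points) |
|---|---|---|---|
| 0% | 80.0% | 80.0% | 0 |
| 3% | 79.7% | 77.0% | 2.7 |
| 5% | 79.5% | 75.0% | 4.5 |
| 10% | 78.9% | 70.0% | 8.9 |
| 15% | 78.3% | 65.0% | 13.3 |

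Over 10% to 30% recorded loss, the gap is 2.5 to 2.9 points at 3% failures and 12.3 to 14.2 at 15%. At 5%, 0.05 × 35 = 1.75 participants give 4.5 points, or 2.6 each, in line with Step 3. The gap is nearly the assumed failure share, so the table shows how the rule behaves and does not predict its effect in this trial.

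**The case against.** The strongest reply has four parts.

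- **No direct contradiction.** The time-to-loss rows carry no estimand, and censoring at rescue is a recognised choice. This stands as far as it goes, but the question being answered is then unstated, and no curve addresses the question that the SAP makes primary for maintenance.
- **Limited importance.** The curves are descriptive and outside the multiplicity scheme. The by-visit maintenance proportions already count these events as failures. The version history gives consistency with the global pivotal studies as the reason for adding the endpoints. All true. It confines the problem to the curves without removing it.
- **Limited exposure.** EASI and IGA are assessed at every maintenance visit and at early termination, so a loss recorded before censoring still counts. For EASI the problem is confined to rescue or drop-out with no recorded loss.
- **Rescue is not always skin failure.** Protocol Section 6.5.1 treats systemic corticosteroids given for an adverse event, such as an asthma exacerbation, as rescue. SAP Section 6.6.1 narrows this to drugs whose recorded indication is rescue therapy, but some such cases may remain. This is why the censoring is called likely, not certainly, informative.

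A reader might also infer that the curves will sit above the by-visit proportions. The documents do not support that. Kaplan-Meier counts the first dip as permanent, while by-visit response can be regained. Suppose that 6 of 36 participants dip below EASI-75 once and recover, and 2 others later have systemic rescue. The curve ends at 30/36 = 83%, and the by-visit proportion at 34/36 = 94%. For IGA, the two also differ in what counts as loss.

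**Conclusion.** The point holds for all three variables. Systemic rescue and discontinuation for lack of efficacy are censored in the time-to-loss analyses but count as failure in the primary maintenance estimand and in the supportive hybrid and composite estimands. For IGA the same is true of escape without a 2-point worsening. Each curve therefore lies at or above the curve under the SAP's own failure definition.

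The size is roughly the share of participants who fail this way without a recorded loss: about 3 points per participant for EASI-75 in a re-randomised Q2W arm, somewhat more for IGA, and nothing if no such event occurs. This rests on the planned Week 16 response rates and on little other censoring. Larger gaps, such as 9 points at 10% failures, depend on rates that the documents do not give. The issue warrants a change to the SAP but does not touch the Week 16 conclusions.

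**What to change.** In SAP Appendix 1, define a composite time-to-loss curve aligned with the maintenance primary estimand:

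- For all three variables, count systemic rescue (as defined in SAP Section 6.6.1) and discontinuation for lack of efficacy as loss on that date.
- For IGA, also count transfer to the Escape Arm as loss. For EASI-50 and EASI-75 it is already an event.
- Censor only discontinuation for other reasons and end of follow-up.

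In Appendix 2, replace N/A with the named estimand. Report the present censoring rule alongside, for comparability with the global studies.

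The cost is SAP wording and one programming flag, with no new data. The curves will be slightly less favourable, and some systemic rescue recorded for an adverse event may count as loss while skin response is maintained. Showing both curves lets the reader see how much depends on the choice.

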	
• Proportion of participants with an Itch NRS score of ≥ 4 points at baseline who achieve a ≥ 4-point reduction from baseline by visit• Proportion of participants with an Itch NRS score of ≥ 4 points at baseline who achieve both EASI-75 and a ≥ 4-point reduction in Itch NRS score from baseline by visit• Proportion of participants with an Itch NRS score of ≥ 4 points at baseline who achieve both an IGA score of 0 or 1 with a ≥ 2-point improvement from baseline, and a ≥ 4-point reduction in Itch NRS score from baseline by visit• Change from baseline in Skin Pain NRS score by visit• Proportion of participants with a Skin Pain NRS score of ≥ 4 points at baseline who achieve a ≥ 4-point reduction from baseline by visit• Change from baseline in percent BSA by visit• Change from baseline in Sleep-Loss score by visit• Proportion of participants achieving a ≥ 4-point improvement in DLQI/CDLQI score from baseline by visit• Proportion of participants achieving DLQI/CDLQI score of 0 or 1 by visit• Change from baseline in DLQI/CDLQI by visit• Change from baseline in POEM by visit• Change from baseline in WPAI-AD score by visit• Change from baseline in HADS score by visit• Change from Baseline in ACQ-5 score to Week 16 in participants who have self-reported comorbid asthma
--	--

	
 • Percentage change from Baseline in SCORAD by visit • Proportion of TCS/TCI-free days over the 16 week and 68-week study periods • Total amount of TCS used over the 16-week and 68-week study periods • Time (days) to TCS/TCI-free use over the 16-week and 68-week study periods

 • To assess the growth of adolescent participants treated with lebrikizumab 	
 • Mean changes in growth parameters (height, weight, and BMI) over the course of treatment

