4.1.6.1.4. Mixed-effects Model for Repeated Measures (MMRM)

Mixed-effects model for repeated measures analyses will be performed on continuous endpoints to mitigate the impact of missing data. This approach assumes missing observations are missing-at-random (missingness is related to observed data) and borrows information from participants in the same treatment arm taking into account both the missingness of data through the correlation of the repeated measurements.

The values subsequent to rescue medication use (i.e., high-potency TCS or systemic AD treatment, defined in [Appendix 13](#)) or treatment discontinuation will be made missing before applying the MMRM model. The MMRM model is described in Section [4.1.1](#).

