Work Productivity and Activity Impairment: Atopic Dermatitis (WPAI-AD)	The Work Productivity and Activity Impairment Questionnaire – Atopic Dermatitis (WPAI-AD) records impairment due to AD during the past 7 days. The WPAI-AD consists of 6 items grouped into 4 domains: absenteeism (work time missed), presenteeism (impairment at work/reduced on the job effectiveness), work productivity loss (overall work impairment/absenteeism plus presenteeism), and activity impairment. Scores are calculated as impairment percentages (Reilly et al. 1993), with higher scores indicating greater impairment and less productivity.	Employment status	Question (Q)1	Single item, missing if missing.
		Change in employment status	Employed at baseline and remained employed: Q1 = 1 at post-baseline visit and at baseline visit. Not employed at baseline and remain unemployed: Q1 = 0 at post-baseline visit and at baseline visit.	Missing if baseline or observed value is missing.
		Percentage of absenteeism	Percent work time missed due to problem: $(Q2/(Q2 + Q4)) * 100$	If Q2 or Q4 is missing, then missing.
		Change from baseline in absenteeism	Change from baseline: observed absenteeism – baseline absenteeism	Missing if baseline or observed value is missing.
		Percentage of presenteeism	Percent impairment (reduced productivity while at work) while working due to problem: $(Q5/10) * 100$	If Q5 is missing, then missing.
		Change from baseline in presenteeism	Change from baseline: observed presenteeism – baseline absenteeism	Missing if baseline or observed value is missing.
		Overall work impairment	Percent overall work impairment (combines absenteeism and presenteeism) due to problem: $(Q2/(Q2 + Q4) + [(1 - Q2/(Q2+Q4)) * (Q5/10)]) * 100$	If Q2, Q4, or Q5 is missing, then missing.

		Change from baseline in work impairment	Change from baseline: observed overall work impairment – baseline overall work impairment	Missing if baseline or observed value is missing.
		Percentage of activity impairment	Percent activity impairment (performed outside of work) due to problem: $(Q6/10)*100$	If Q6 is missing, then missing.
		Change from baseline in activity impairment	Change from baseline: observed activity impairment – baseline activity impairment	Missing if baseline or observed value is missing.

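### The WPAI-AD overall work impairment score is set to missing when item Q5 is blank, even where the SAP's own formula fixes it at 100% without Q5

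*SAP*

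**What the plan says.** The WPAI-AD block of SAP Section 6.1 (Appendix 1) derives three work-related scores.

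- Absenteeism is 100 × Q2/(Q2 + Q4), with the rule "If Q2 or Q4 is missing, then missing". Q2 is therefore the work time lost to AD, and Q4 is the rest of the work time.
- Presenteeism is 100 × Q5/10, described as "Percent impairment (reduced productivity while at work) while working due to problem". It needs Q5 only.
- Overall work impairment combines the two: 100 × {Q2/(Q2 + Q4) + [1 − Q2/(Q2 + Q4)] × Q5/10}. Its rule is "If Q2, Q4, or Q5 is missing, then missing", with no exception for Q4 = 0.

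For the change scores the rule is "Missing if baseline or observed value is missing". The endpoint, "Change from baseline in WPAI-AD score by visit", is listed under Other Secondary in SAP Section 1.1. Appendix 2 analyses it by MMRM against placebo in the Induction Period, and by descriptive statistics with LOCF in the Maintenance Primary Population.

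**The concern.** Q5 asks about performance while at work. A participant who worked no hours in the past 7 days because of AD has nothing to rate and may leave it blank. Such a participant has lost all work time to AD and would score the maximum on overall impairment, yet the rule records the score as missing. The same participant keeps a 100% absenteeism score, so the component survives and the composite that contains it is dropped.

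The values lost by this route are all at the top of the scale, and the analyses treat the gap as follows.

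- Baseline: the change score is lost at every later visit, so someone who improves from 100% contributes nothing.
- After baseline, Induction Period: the MMRM in SAP Section 4.1.6.1.4 assumes missing at random, although this gap arises because the value is 100%.
- After baseline, Maintenance Period: LOCF carries forward an earlier value, which can only be equal to or lower than 100%.

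**Working it through.** There is no stated figure to reproduce; the check is of the formula against the rule beside it.

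**Step 1. Formula with no hours worked.** Inputs: the overall work impairment formula in SAP Appendix 1, with Q4 = 0 and Q2 > 0.

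Q2/(Q2 + 0) = 1, so the score is 100 × [1 + (1 − 1) × Q5/10] = 100 for any Q5.

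Evaluating the formula at Q2 = 1, 8, 20 and 40 hours, for all 11 values of Q5 from 0 to 10, gives 100.0 every time.

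**Step 2. Formula with some hours worked.** Here Q5 does matter:

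| Q2 | Q4 | Q5 = 0 | Q5 = 5 | Q5 = 10 |
|---|---|---|---|---|
| 39 | 1 | 97.5 | 98.8 | 100 |
| 20 | 20 | 50 | 75 | 100 |
| 8 | 32 | 20 | 60 | 100 |
| 0 | 40 | 0 | 50 | 100 |

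When Q4 > 0, setting the score to missing for a blank Q5 is justified. The rule goes too far only in the case of Step 1.

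**Step 3. No hours at all.** Q2 = Q4 = 0 divides by zero. The SAP gives no rule for it; it is a separate case, but the same line can cover it.

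**Step 4. Can Q5 be blank?** The EASI, BSA, SCORAD and HADS rows of Appendix 1 say that partial assessments cannot be saved. The WPAI-AD rows do not, and their rule provides for a missing Q5. For the DLQI work item, Appendix 1 accepts a blank 7B as valid when 7A is not answered No, and it loses the work domain only if 7A is missing, or if 7A is No and 7B is missing. WPAI-AD has no matching provision.

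**Step 5. Possible size (every rate and mean here is assumed).** The documents give no employment rate, no rate of zero-hours weeks and no WPAI-AD mean.

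- Suppose 60% are employed: 0.60 × 280 = 168 overall, and 0.60 × 80 = 48 in an arm of 80. If 1% to 3% of the 168 worked no hours because of AD, that is 1.7 to 5.0, or about 2 to 5 participants per visit, provided all of them leave Q5 blank. If none do, the number is 0.
- Suppose the 48 have a mean of 35% including one value of 100%. Dropping it leaves (48 × 35 − 100)/47 = 1580/47 = 33.6, a fall of 65/47 = 1.4 points.
- More generally, if a fraction f is at 100% and dropped, and the rest average m, the observed mean is too low by f × (100 − m). For f = 1% and m = 40% this is 0.6 points; for f = 10% and m = 20% it is 8.0 points.

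**The case against.** The strongest objection is that the harm depends on a premise the documents do not contain. Neither protocol Section 8.1.2 nor SAP Appendix 1 reproduces the questionnaire items, response options or skip instructions. WPAI-AD is completed on a tablet, and the SAP version history records that a POEM rule was removed because the situation cannot arise with electronic capture. If the tablet forces an answer to Q5, the plan already returns 100% and nothing is lost. This stands: the frequency is unknown and may be zero. It does not remove the point, because the SAP's rule itself allows for a blank Q5.

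It may also be said that requiring every component of a composite is an ordinary, reproducible convention. That too is fair, and the point is therefore a gap in a missing-data derivation. The formula contains no arithmetic error. Nor can the SAP be said to depart from the published scoring it cites, which is not available here.

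A reader might infer that the rule removes exactly the most impaired participants. It does not: anyone with Q4 > 0 and Q5 = 10 also scores 100% and is kept, and those affected keep their absenteeism score, and their activity impairment score if Q6 is answered.

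A reader might also infer that the lebrikizumab-placebo comparison is biased in a known direction. The documents do not support that. The illustration concerns raw means, whereas the Induction analysis compares changes from baseline. A baseline loss occurs before treatment in whichever arm it falls, and the Maintenance analysis makes no comparison.

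**Conclusion.** The point holds in a conditional form. For Q4 = 0 and Q2 > 0 the SAP's formula gives 100% whatever Q5 is, and its rule still sets the score to missing if Q5 is blank. That much follows from the SAP alone. Whether any score is lost depends on participants with no worked hours leaving Q5 blank, which is plausible but not documented.

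The reach is small: one of four WPAI-AD domains, within an other secondary endpoint that lies outside the hypotheses listed in SAP Section 2. No primary or major secondary conclusion is touched. The 1.4-point illustration rests wholly on assumed inputs, and no size or direction can be given for the treatment difference. This is a minor improvement, worth making because it costs almost nothing.

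**What to change.** Replace the missing-component rule for overall work impairment in SAP Appendix 1 with:

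- if Q4 = 0 and Q2 > 0, overall work impairment = 100% regardless of Q5;
- if Q2 + Q4 = 0, missing;
- otherwise, missing if Q2, Q4 or Q5 is missing.

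Leave presenteeism missing when Q5 is missing, since a participant who did not work has no on-the-job impairment to report.

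The cost is one line in Appendix 1 and the matching line of derivation code. No new data are needed. If Q5 turns out always to be answered, no participant's score changes.
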